### 10.6 MEASURES TO MINIMIZE BIAS

---

#### 10.6.1 ENROLLMENT/ RANDOMIZATION/ MASKING PROCEDURES

One hundred individuals with PSACH will be enrolled in the study and then randomized to receiving resveratrol or placebo first based on randomization assignment by biostatistician. We will not replace enrollees that drop out as we have statistical power to lose 10% of the cohort and still determine whether the supplement provides relief of pain. All study participants will be blinded to the study drug. All study investigators and analysts will be blinded to the study drug with the exception of the study coordinator who will be responsible for mailing out the study medications.

---

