## 4 STUDY DESIGN AND ENDPOINTS

### 4.1 DESCRIPTION OF THE STUDY DESIGN

The study has a 2x2 crossover design. Participants will take either the placebo or resveratrol for 90 days followed by a 30 day washout period and the placebo or resveratrol for the last 90 days. 30 day washout period was chosen in order to eliminate any carry over from resveratrol as it is recommended to avoid resveratrol 2 weeks prior to surgery suggesting that carry over could potentially be as long as 2 weeks (<http://www.webmd.com/vitamins-supplements/ingredientmono-307-resveratrol.aspx?activeingredientid=307>; <http://ww5.komen.org/BreastCancer/Resveratrol.html>). Participants will be mailed a 30 or 90 day (for international participants) supply of placebo or resveratrol which they will receive 5 days before the end of each 30 day period (not applicable for international participants). Participants will keep daily pain log of pain and activity levels during the entire 210 day study period. We recognize that this is a long period of time however this population is highly motivated because 1) their pain is not systematically treated, 2) currently available over the counter NSAIDs, frequently used to control pain, cause gastrointestinal issues when used for prolonged periods and 3) participants reached through Little People of America and the PSACH facebook page are actively seeking solutions to control pain. This is being co-ordinated by a single center and will enroll 30 PSACH individuals. Because this is a rare condition, participants from 18 years - to 70 years will be enrolled.

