### 10.5 SAMPLE SIZE

Although studies haven't quantified pain variability in PSACH, other studies have utilized a pain VAS and have reported standard deviation (SD) of the difference between scores for the same patient of about 10-15 on a 1-100 scale. In addition, previous research by one of the investigators has suggested that a strong placebo effect can be present in studies using the pain VAS at a magnitude of about 20 on a 1-100 scale. Assuming a similar degree of variability in our study population and considering the placebo effect as reported, with a sample size of 30 participants at a Type I error rate of 5%, the minimal detectable difference would be 2.8 units at a SD of 10 and power of 80%, 4.25 at a SD of 15 and power of 80%, 3.3 at a SD of 10 and power of 90%, and 4.9 at a SD of 15 and power of 90%. Considering that there are about 300 potential patients that can be approached through the "Little People of America" support group and the Facebook PSACH group, we should be able to recruit into the study at least half of those highly motivated and invested individuals. We should be able to achieve our sample size of 30 patients for this study, even assuming a considerably high 33% attrition rate. We will screen 60 to enroll 30.

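### The 10% loss tolerance behind the no-replacement rule (10.6.1) has no supporting calculation and does not fit the 10.5 power figures, which match 100 complete pairs, not 30, and allow for no loss

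*Combined protocol and SAP*

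**What the plan says.** Section 10.6.1 rules out replacement: "We will not replace enrollees that drop out as we have statistical power to lose 10% of the cohort". The sentence goes on to tie this tolerance to being able to tell whether the supplement relieves pain. The same paragraph sets the cohort at 100: "One hundred individuals with PSACH will be enrolled in the study and then randomized".

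Elsewhere the cohort is 30. Section 4.1 has "This is being co-ordinated by a single center and will enroll 30 PSACH individuals", and section 10.5 ends with "We will screen 60 to enroll 30".

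Section 10.5 holds the only power calculation. It takes a "standard deviation (SD) of the difference between scores for the same patient of about 10-15 on a 1-100 scale". For 30 participants and a 5% type I error rate it then reports that "the minimal detectable difference would be 2.8 units at a SD of 10 and power of 80%, 4.25 at a SD of 15" (the second also at 80% power), with 3.3 and 4.9 as the counterparts at 90% power. It adds that a sample of 30 should be achievable "even assuming a considerably high 33% attrition rate".

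The effect of interest is on a different scale. Section 10.1 treats at least 2 units on the 11-point scale as a true change. Section 10.2 hypothesises a difference of 2.8 points on 0-10.

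**The concern.** In a 2x2 crossover the treatment contrast comes mainly from people with data in both periods. A rule against replacing dropouts therefore fixes how many complete pairs the trial can have, and here the rule is justified by a specific numerical property.

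That property is not derived anywhere. The figures it would have to come from are computed with every participant counted as complete, and they do not belong to the 30 participants for whom they are stated. A second attrition figure, 33%, sits in 10.5 and is not reconciled with the 10%. The protocol also does not say whether 30 means enrolled or completers.

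At stake is whether the detectable differences in 10.5 describe the trial that will be run, and whether anyone can judge how much loss it can absorb.

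**Working it through.** **Inputs.** From 10.5: SD of the within-patient difference 10 or 15 (1-100 scale), type I error 5%, power 80% or 90%, n = 30. From 10.6.1: n = 100 and a 10% loss. From 10.5: 33% attrition. The plan does not state sidedness; two-sided is assumed. Dropouts are assumed to contribute no pair.

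**Formula.** For paired differences, detectable difference ≈ (z for 1 − α/2 + z for power) × SD / √n. The tables use the exact noncentral-t version, which is slightly larger.

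**Reproducing the plan's figures.** SD 10, 80% power, normal approximation:
- n = 100: (1.960 + 0.842) × 10 / 10 = 2.80, which is the stated 2.8.
- n = 30: 28.0 / 5.477 = about 5.11, which is not 2.8.

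Detectable differences from the noncentral t:

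| Case | Stated for 30 | n=100 | n=90 | n=30 | n=27 | n=20 |
|---|---|---|---|---|---|---|
| SD 10, 80% | 2.8 | 2.83 | 2.99 | 5.29 | 5.60 | 6.60 |
| SD 15, 80% | 4.25 | 4.24 | 4.48 | 7.94 | 8.40 | 9.91 |
| SD 10, 90% | 3.3 | 3.27 | 3.45 | 6.12 | 6.48 | 7.64 |
| SD 15, 90% | 4.9 | 4.91 | 5.18 | 9.19 | 9.72 | 11.47 |

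Solving for n in the four stated cases gives 102.1, 99.7, 98.4 and 100.4. Other readings at n = 30 do not rescue the figures. A one-sided test gives 4.65, 6.97, 5.47 and 8.21. Treating the SD as within-subject, or the design as 15 per arm in parallel, makes the differences larger still. Halving the SD gives 2.65, 3.97, 3.06 and 4.59.

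**Power for the stated differences after loss.** A 10% loss leaves 0.90 × 30 = 27 or 0.90 × 100 = 90. A 33% loss leaves about 20 or 67.

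| Case | 100 | 90 | 67 | 30 | 27 | 20 |
|---|---|---|---|---|---|---|
| SD 10, 2.8 | 79.2% | 74.8% | 61.7% | 31.7% | 28.8% | 22.1% |
| SD 15, 4.25 | 80.1% | 75.8% | 62.8% | 32.3% | 29.4% | 22.5% |
| SD 10, 3.3 | 90.5% | 87.2% | 75.9% | 41.6% | 37.9% | 28.8% |
| SD 15, 4.9 | 89.9% | 86.6% | 75.0% | 40.9% | 37.3% | 28.4% |

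So the full 100 are used up in reaching 80% and 90%, and at 30 the shortfall exists before anyone drops out.

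**Enrolment allowance.** Keeping 30 completers would need 30 / 0.90 = 33.3, so 34 enrolled, or 30 / 0.67 = 44.8, so 45 enrolled. The plan enrols 30.

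**Against the target effects on 0-10.** Dividing the SD by 10 gives 1.0-1.5 points. At 80% power the detectable difference is 0.56-0.84 points with 27 completers and 0.66-0.99 with 20. At 90% power it is 0.65-0.97 and 0.76-1.15. Power for 2 or 2.8 points is above 99.9% with 27 completers and at least 99.9% with 20. Because 10.5 concedes that pain variability in PSACH has not been quantified, an SD of 3 points was also tried as an assumption: power for 2 points is 91.5% with 27 completers and 80.7% with 20.

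**The case against.** The strongest reply is that the wrong benchmark is being used. The 10% sentence concerns whether pain relief can be determined, and the plan expresses relief as 2 or 2.8 points on 0-10. A minimal detectable difference is by definition the value at which power is exactly the nominal one. Lack of slack there says nothing about slack for a much larger effect. On the rescaled SDs the trial could lose 10%, or even 33%, and hardly notice. This stands. A reader might infer from the tables above that the tolerance claim is false, or that 30 participants are too few for the stated hypothesis. The documents support neither: the 2.8 in 10.2 is on the 0-10 scale, and the 2.8 in 10.5 goes with an SD of 10 on a 1-100 scale, so it is about 0.28 points on 0-10.

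A reader might also infer that the plan expects 33% of randomised participants to drop out. It does not say so. The 33% is worded as a pessimistic case and follows directly on the hope of recruiting at least half of about 300 people. It may apply to that pool: 150 × 0.67 = 100.5. The 20-completer case is therefore conditional on the 33% applying after enrolment.

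Finally, the mismatch between 30 and 100 is the larger error, and dropout adds little to it (32% to 29% in the first case). That is true, but settling the enrolment number alone would leave the 10% underived, the 10% and 33% unreconciled, and no allowance for loss.

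**Conclusion.** The tolerance in 10.6.1 is unsupported and inconsistent with 10.5; it is not demonstrated to be wrong for the plan's target effects. The detectable differences in 10.5 are wrong as written for 30 participants. The correct values are nearly twice as large (5.29 / 2.8 = 1.9), and the stated ones have 32-42% power. A 10% loss takes power below the stated 80% or 90% at either cohort size: to 29-38% with 27 of 30, or 75-87% with 90 of 100.

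This rests on a two-sided 5% test and a paired analysis of completers with 10.5's SDs. It gives no credit for repeated monthly averages or for partial data in the mixed model. The conclusion about the 0-10 effects also assumes that the SD scales by a factor of 10. The correction is worth making because the figures cannot stand, although the practical risk to power for a 2-point or 2.8-point effect is small on these SDs.

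**What to change.** In 10.5, 10.6.1 and 4.1:
- State one enrolment number, and say whether it means enrolled or completers.
- Use a single dropout assumption in 10.5 and 10.6.1. If the 33% refers to recruitment and not to loss after enrolment, say so.
- Restate the detectable differences for the expected completers, on the 1-100 scale and with 0-10 equivalents. For SD 10 and 15, 27 of 30 gives 5.6 and 8.4 at 80% power and 6.5 and 9.7 at 90% (about 0.56-0.97 points). For 20 of 30 the values are 6.6 and 9.9, then 7.6 and 11.5 (about 0.66-1.15 points).
- State the sidedness of the 5%.
- Replace the 10% sentence with a tolerance computed against the stated target effect on the 0-10 scale, giving the SD used.

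The cost is wording and recomputed figures, with no added patients and no change to the no-replacement rule itself. The downside is that the published detectable differences become less favourable. Giving them on the 0-10 scale as well shows that they remain below the 2-point threshold.

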#### 10.6.2 EVALUATION OF SUCCESS OF BLINDING

At the end of each study period, all study subjects will be asked to respond to a single question asking them to identify if they were on the study drug or placebo during the previous intervention period. This data will be analyzed after 20, 40 and all subjects have completed the study to evaluate the success of blinding.

#### 10.6.3 BREAKING THE STUDY BLIND/PARTICIPANT CODE

The study blind/participant code will be broken only in the case of an AE or SAE if the DSMB deems it important for appropriate assessment of the event. In this scenario, the study coordinator will communicate with the DSMB regarding the randomization arm of the particular participant. Other study team members will remain blinded.

### 11 SOURCE DOCUMENTS AND ACCESS TO SOURCE DATA/DOCUMENTS

All study documents and data will be kept securely by the study coordinator. All electronic data will be password-protected and stored on HIPAA compliant NAS servers at the McGovern Medical School University of Texas Health Science Center at Houston. All hard-copies of the ICFs, CRFs, consent forms, pain logs, HRQoL assessments and other data collected from patients will be stored in a locked filing cabinet on the premises of the McGovern Medical School at the University of Texas Health Science Center at Houston. Access to all these records will be limited to the study coordinator. The coordinator will tabulate and aggregate information for consumption by the DSMB, study team and IRB if applicable.

### 12 QUALITY ASSURANCE AND QUALITY CONTROL

Quality control procedures will be implemented by the study-coordinator to monitor all study documentation for completeness and accuracy. Any missing data or data anomalies will be communicated to the principal investigator for clarification/resolution.

The investigational site will provide direct access to all trial related sites, source data/documents, and reports for the purpose of monitoring and auditing, and inspection by any local and regulatory authorities.

### 13 ETHICS/PROTECTION OF HUMAN SUBJECTS

#### 13.1 ETHICAL STANDARD

The investigators will ensure that this study is conducted in full conformity with Regulations for the Protection of Human Subjects of Research codified in 45 CFR Part 46, 21 CFR Part 50, 21 CFR Part 56, and/or the ICH E6.]

#### 13.3 INFORMED CONSENT PROCESS

##### 13.3.1 CONSENT/ASSENT AND OTHER INFORMATIONAL DOCUMENTS PROVIDED TO PARTICIPANTS

Consent forms describing in detail the study agent, study procedures, and risks are given to the participant and written documentation of informed consent is required prior to ascertaining diagnostic information and/or starting intervention/administering study product. The following consent materials are submitted with this protocol : 1) adult consent form.

##### 13.3.2 CONSENT PROCEDURES AND DOCUMENTATION

Study participants and/or their family members will be informed of risks and possible benefits of participation in this study. Consent forms will be IRB-approved and the participant will be asked to read and review the document. The investigator/study coordinator will explain the research study to the participant and answer any questions that may arise. All participants must be able to communicate in English and they will receive a verbal explanation in terms suited to their comprehension of the purposes, procedures, and potential risks of the study and of their rights as research participants. Participants will have the opportunity to carefully review the written consent form, discuss with other family members and ask questions prior to signing. The participant will sign the informed consent document prior to any participation in the study and mail the consent form to the study coordinator in a provided self-addressed stamped envelope or scan/photograph and email to study coordinator. The participants may withdraw consent at any time throughout the course of the trial. A copy of the informed consent document will be given to the participants for their records or if the participant has their original they will retain this copy for their records. The rights and welfare of the participants will be protected by emphasizing to them that the quality of their medical care will not be adversely affected if they decline to participate in this study.

#### 13.4 PARTICIPANT AND DATA CONFIDENTIALITY

The study protocol, documentation, data, and all other information generated will be held in strict confidence. No information concerning the study or the data will be released to any unauthorized third party without prior written approval of the principal investigator.

Representatives of the IRB may inspect all documents and records required to be maintained by the principal investigator, for the participants in this study. The clinical study site will permit access to all records.

The study participant's contact information will be securely stored at each clinical site for internal use during the study. At the end of the study, all records will continue to be kept in a secure location for 10 years.

##### 13.4.1 RESEARCH USE OF STORED HUMAN SAMPLES, SPECIMENS OR DATA

No human samples or specimens will be collected during this study

Data collected will be analyzed to determine if resveratrol has any benefit for pain in PSACH.

Storage: Access to stored data will be limited using password electronic protection and locked file cabinets. Data will be stored using codes assigned by the investigators. Data will be kept in password-protected computers. Only investigators will have access to the samples and data.

#### 13.5 FUTURE USE OF STORED SPECIMENS

N/A.

### 14 DATA HANDLING AND RECORD KEEPING

#### 14.1 DATA COLLECTION AND MANAGEMENT RESPONSIBILITIES

Pain logs will be mailed or emailed to the study coordinator. The study coordinator will also be responsible for the data collection and storage of the documents in a secured location.

#### 14.2 STUDY RECORDS RETENTION

All study documentation will be kept in a secure location for 10 years and then destroyed.

#### 14.3 PROTOCOL DEVIATIONS

As a result of any protocol deviation, corrective actions will be developed by the PI and implemented promptly. The study IRB will be notified of any protocol deviation within 10 working days of the deviation. The deviations will also be logged in a "Protocol Deviation Log" which will be part of the study quality monitoring plan.

These practices are consistent with ICH E6:

- 4.5 Compliance with Protocol, sections 4.5.1, 4.5.2, and 4.5.3
- 5.1 Quality Assurance and Quality Control, section 5.1.1
- 5.20 Noncompliance, sections 5.20.1, and 5.20.2.

#### 14.4 PUBLICATION AND DATA SHARING POLICY

This study is not funded. We will submit a manuscript with the findings to a peer-reviewed journal. In addition, the clinical trial be registered with *clinicaltrials.gov*.

### 15 STUDY ADMINISTRATION

#### 15.1 STUDY LEADERSHIP

The Steering Committee, composed of Drs. [name] and [name], who are the PIs, will govern the conduct of the study. The Steering Committee meets on a weekly basis. Study progress, including recruitment rates protocol deviations, quality monitoring and DSMB reports will be assessed by the Steering Committee on an annual basis.

### 16 CONFLICT OF INTEREST POLICY

This project is independent of any actual or perceived influence, such from the pharmaceutical industry. We are using an over the counter supplement that is purchased and there is no financial contribution from the manufacturer.

**APPENDIX**

Version	Date	Significant Revisions
